Hypothesis: Treatment with glargine U300 will result in equivalent glycemic control in hospitalized patients with T2D. Glargine U300 will result in lower number of hypoglycemia compared to glargine.

Aim 2: To determine differences in glycemic control after hospital discharge between treatment with glargine U300 and glargine U100 in medicine and surgery patients T2D. Patients with poorly controlled diabetes ($HbA1c \geq 7.5\%$) enrolled in Aim 1 will be invited to participate in this open label prospective outpatient study. The total duration of the study is 3 months. Patients with an $HbA1c$ between 7.5% and 10% will be discharged on preadmission oral antidiabetic agents plus glargine U300 and U100 once daily. Patients with an admission $A1C \geq 10\%$ will be discharged on basal bolus regimen with glargine and glulisine insulin before meals.

Hypothesis: treatment with glargine U300 and U100 will result in a similar improvement in HbA1c levels after hospital discharge. Glargine U300 will result in lower number of hypoglycemia compared to U100.

II. BACKGROUND AND CURRENT STATUS OF WORK IN THE FIELD.

Inpatient glycemic control in non-ICU setting. A large body of evidence has shown that in hospitalized patients, the presence of hyperglycemia and diabetes is associated with increased risk of complications and death (1-6, 28-31). Several randomized multi-center trials have shown that the use of basal bolus insulin regimen result in improved glycemic control and reduced rate of hospital complications compared to sliding scale regular insulin (SSI) in patients with T2D (12-14). We have reported that treatment with basal and basal bolus regimens using glargine U100 results in greater improvement in BG control and a reduction in the frequency of hospital complications including postoperative wound infection, pneumonia, bacteremia, and acute renal and respiratory failure compared to SSI treatment.(16, 17, 32, 33) In addition, the use of basal bolus regimen with glargine U100 is safe with low rate of hypoglycemic events. Based on these studies and others, clinical practice guidelines for the management of hyperglycemia in non-ICU setting have favored the use of basal prandial insulin regimens with insulin analogs for most inpatients with T2D (6, 19, 31).

Efficacy and safety of new glargine U-300 insulin:

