
Group 1. Basal bolus with glargine U300 once daily and glulisine insulin before meals (n=90).

Group 2. Basal bolus with glargine U100 once daily and glulisine insulin before meals (n=90).

IV.d. Basal Bolus Insulin Protocol.

Patients will be treated with a basal bolus insulin regimen as previously reported (15, 16, 39). In brief, subjects treated with insulin prior to admission will receive 80% of the total daily outpatient insulin dose given. Insulin naïve patients will discontinue oral agents and will receive a starting total daily dose (TDD) of 0.4 U/kg/day for BG between 140 mg/dl and 200 mg/dL and 0.5 U/kg/day for BG between 201 mg/dl and 400 mg/dL. The starting TDD will be reduced to 0.3 U/kg/day in patients \geq 70 years or with a GFR < 60 ml/min. Both groups will be treated with bolus regimen given half of TDD as basal (glargine U300 or U100) once daily and half as insulin glulisine divided in three equal doses before meals. Patients with poor oral intake or to be kept NPO will receive the basal dose, but prandial dose will be held (32). Insulin dose will be adjusted daily to maintain a fasting and pre-dinner BG between 80 mg/dl and 180 mg/dl.

IV. e Treatment randomization. This is an open label randomized controlled trial. Patients will be randomized 1:1 consecutively using a computer generated randomization table provided by [name], statistician at the Emory School of Public Health. The randomization table will be mailed to the research pharmacist at each institution who will be in charge of the randomization and group assignment. A research pharmacist at each institution will follow a computer-generated block randomization table based on prior insulin use (yes/no).

IV.f TREATMENT PROTOCOL - Basal Bolus Insulin Regimen with Glargine Once Daily plus Glulisine before Meals

Patients Treated with Insulin Prior to Admission

- Discontinue oral antidiabetic drugs on admission.

Subjects treated with insulin prior to admission will receive 80% or 100% of the total daily dose (TDD) given as basal bolus regimen. **Starting Insulin Doses:**

- Randomization BG <200mg/dl-give 80% of the TDD*
- Randomization BG>200mg/dl-give 100% of the TDD*
- Half of TDD will be given as basal (glargine U300 or U100) and half as rapid-acting insulin.
- Glargine U300 and U100 will be given once daily, at the same time of the day.
- Patients will receive the full-dose of glargine (even if NPO) the day of surgery or diagnostic procedure(s).

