- Glulisine insulin will be given in three equally divided doses before each meal. To prevent hypoglycemia, if a subject is not able to eat, glulisine insulin dose will be held.

* If patient was on basal only therapy consider adding prandial dose as calculated above.

Insulin Naïve Patients Treated with Oral Agents or GLP1-RAs Prior to Admission

- Discontinue oral antidiabetic drugs on admission.
- Starting total daily insulin dose:
 - 0.4 U/Kg/day when randomization BG between 140-200 mg/dL
 - 0.5 U/Kg/day when randomization BG between 201-400 mg/dL
 - Reduce TDD to 0.3 units per kg in patients ≥ 70 years of age and/or with an eGFR < 60 ml/min.
- Half of TDD will be given as glargine U300 or U100 and half as glulisine.
- Glargine will be given once daily, at the same time of the day.
- Patients will receive the full-dose of glargine insulin (even if NPO) the day of surgery or diagnostic procedure(s).
- Glulisine insulin will be given in three equally divided doses before meals. To prevent hypoglycemia, if a subject is not able to eat, the dose of glulisine will be held.

Supplemental insulin. Glulisine insulin will be administered following the “supplemental/correction insulin scale” protocol (Appendix 1).

- If a patient is able and expected to eat most of his/her meals, supplemental insulin will be administered before meals and at bedtime following the “usual” dose of the insulin scale protocol.
- If a patient is not able to eat, supplemental insulin will be administered every 6 hours following the “sensitive” dose of the supplemental insulin scale protocol.

Basal Insulin adjustment.

- Daily basal (glargine U300 and U100) insulin dose will be adjusted as follow:

- If the fasting and pre-dinner BG is between 100 - 140 mg/dl in the absence of hypoglycemia the previous day: no change
- If the fasting and pre-dinner BG is between 141 - 180 mg/dl in the absence of hypoglycemia: increase basal insulin by 10% every day
- If the fasting and pre-dinner BG is 181- 299 mg/dl in the absence of hypoglycemia the previous day: increase basal insulin (glargine) dose by 20% every day
- If the fasting and/or pre-dinner BG is ≥ 300 mg/dl in the absence of hypoglycemia the previous day: increase basal insulin (glargine) dose by 30% every day
- If the fasting and pre-dinner BG is between 70 - 99 mg/dl in the absence of hypoglycemia: decrease TDD (basal and prandial) insulin dose by 10% every day

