We plan to study a total of 180 randomized patients with a known history of T2D, age > 18 years, treated with diet alone, any combination of oral antidiabetic agents, GLP1-RA (except long-acting agents: albiglutide, albiglutide and weekly exenatide) or insulin therapy (except degludec or glargine U300). Patients included within this study will be determined by the set of inclusion and exclusion criteria.

VI.b. Inclusion Criteria:

1. Males or females between > 18 years admitted to a general medicine or surgical service.
2. Known histories of T2D treated with either diet alone, oral monotherapy, any combination of oral antidiabetic agents, short-acting GLP1-RA (exenatide, liraglutide) or insulin therapy with the exception of degludec and glargine U300.
3. Subjects must have a randomization BG > 140 mg and < 400 mg/dL without laboratory evidence of diabetic ketoacidosis (bicarbonate < 18 mEq/L, pH < 7.30, or positive serum or urinary ketones).

VI.c. Exclusion Criteria:

1. Subjects with increased BG concentration, but without a known history of diabetes.
2. Admission or pre-randomization BG ≥ 400 mg/dl
3. Patients treated with degludec or glargine U300, or with long-acting weekly GLP1-RA (weekly exenatide, dulaglutide or albiglutide).
4. Patients with acute critical or surgical illness admitted to the ICU or expected to require admission to the ICU.
5. Patients with clinically relevant hepatic disease (diagnosed liver cirrhosis and portal hypertension), corticosteroid therapy, or impaired renal function (eGFR < 30 ml/min).
6. Mental condition rendering the subject unable to understand the nature, scope, and possible consequences of the study.
7. Female subjects who are pregnant or breast-feeding at time of enrollment into the study.

VI.d. Withdrawal Criteria

1. The subject may withdraw at will at any time.
2. The subject may be withdrawn from the trial at the discretion of the investigator due to a safety concern or if judged non-compliant with trial procedures or included in contravention to the inclusion and/or exclusion criteria.
3. Subject admitted to the ICU who required continuous intravenous insulin infusion to maintain glycemic control.
4. Pregnancy or intention to become pregnant.
5. Treatment with oral or injectable corticosteroid (equivalent or higher than prednisone 5mg/day), parenteral nutrition and immunosuppressive treatment after randomization.

Treatment Failure Criteria

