per kg of body weight) in patients ≥ 70 years of age and/or eGFR < 60 ml/min. To avoid hypoglycemia, the total daily dose of insulin will be decreased by 10% for BG between 70-99 mg/dl and by 20% after each episode of hypoglycemia (BG < 70 mg/dl). In addition, in patients treated with insulin at home, the TDD of insulin will be reduced by 20% on admission and the attending physician may further reduce insulin dose in the presence of severe hypoglycemia.

Hypoglycemia will be treated with dextrose infusion. Dextrose 50% solution will be given for glucose values < 70 mg/dl. If the patient is awake, 25 ml (1/2 amp) will be given IV or oral juice/snack (crackers) as per protocol. If the patient is not awake: 50ml (1 amp) will be given STAT. Blood glucose levels will be repeated in 15 minutes and dextrose administration will be repeated as needed for values < 70 mg/dl.

XI. Inclusion of women.

We anticipate that ~50% of the study subjects will be female. Absence of pregnancy must be demonstrated by blood or urine testing prior to randomization (in female subjects of child bearing potential only). Glargine U300 and U100 have not been approved during pregnancy.

XII. Inclusion of minorities.

Patients will not be excluded based on race or ethnic origin. We anticipate that approximately one-third of patients will be African Americans, Hispanics, and Caucasians.

XIII. Inclusion of children.

No patients under the age of 18 will be recruited in this study.

XIV. Payment for participation.

Participation in this study is voluntary. Patients will receive one hundred dollars (\$100.00) during the hospital stay. If a participant should stop participation before completion, the payment will be prorated at \$10.00 per day. Participants will receive seventy- five dollars (\$75.00) after each clinic visit at 1 and 3 months after discharge. Total compensation will be two hundred and fifty dollars (\$250.00).

XV. Financial conflict of interests.

This study receives support from Sanofi. [name] serves as a consultant to Sanofi and receives compensation for these services. The terms of this arrangement have been reviewed and approved by Emory University in accordance with its conflict of interest policies.

XVI. Pharmacovigilance specifications

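### The starting insulin dose at randomization BG above 200 mg/dl, and the discharge regimen at A1C of 10% or more, are each stated in conflicting ways

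*Combined protocol and SAP*

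**What the plan says.** **Starting dose, patients on insulin before admission**

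- IV.f Treatment Protocol opens with two possible doses: "Subjects treated with insulin prior to admission will receive 80% or 100% of the total daily dose (TDD) given as basal bolus regimen". It then splits by glucose at randomization: "Randomization BG <200mg/dl-give 80% of the TDD" and "Randomization BG>200mg/dl-give 100% of the TDD".
- IV.d Basal Bolus Insulin Protocol, a short summary, gives one figure: "subjects treated with insulin prior to admission will receive 80% of the total daily outpatient insulin dose given".
- X.a Hypoglycemia lists this among its measures against hypoglycemia: "in patients treated with insulin at home, the TDD of insulin will be reduced by 20% on admission".
- The inclusion criteria in VI.b set the glucose range: "Subjects must have a randomization BG > 140 mg and < 400 mg/dL".

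**Discharge, admission A1C of 10% or more**

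- Aim 2 under Specific Aims says these patients "will be discharged on basal bolus regimen with glargine and glulisine insulin before meals". It sets no condition on earlier therapy and gives no dose.
- V.b Insulin Discharge algorithm splits by earlier therapy. Patients on oral drugs, with or without basal insulin, go home on those drugs with glargine at 80% of the inpatient daily dose. Basal bolus is an exception, mainly where oral drugs are contraindicated. Patients with no earlier drug treatment go home on half of their inpatient basal dose, with no A1C condition.

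**The concern.** Take a home-insulin patient randomized at 250 mg/dl. Following IV.f departs from IV.d and X.a; following X.a departs from IV.f. The same holds at discharge for a patient on oral drugs with an A1C of 11%, between Aim 2 and V.b. The text gives no order of precedence.

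Two things are at stake. First, X.a leads its readers, including the IRB, to believe that every home-insulin patient starts at a reduced dose, and above 200 mg/dl the treatment protocol does not do this. Second, hypoglycemia is named in Aim 1 and is a secondary outcome in both aims, in an open-label trial at several sites. If staff have to choose between written rules, the choice is made with the arm known, and adherence cannot be judged cleanly. This is a possibility, not something the documents show to have happened.

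The discharge regimens are not interchangeable on the plan's own account. The background section reports hypoglycemia in about 30% of patients on oral drugs plus basal insulin and above 40% on basal bolus (V.a says close to 40%). Regimen in that study depended on HbA1c, so the gap does not measure the effect of this contradiction.

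**Working it through.** No sample-size or power figure is involved. The check sets the rules side by side and computes the dose ratio.

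**1. Starting dose, share of home total daily dose (TDD)**

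| Randomization BG | IV.f | IV.d summary | X.a |
|---|---|---|---|
| Below 200 mg/dl | 80% | 80% | 100% − 20% = 80% |
| Exactly 200 mg/dl | no rule | 80% | 80% |
| Above 200 mg/dl | 100% | 80% | 80% |

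The sections agree below 200 mg/dl and conflict above it. The value of exactly 200 is a boundary gap in IV.f. The insulin-naive rule has no such gap: "0.4 U/Kg/day when randomization BG between 140-200 mg/dL".

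**2. Size of the starting-dose conflict**

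- Ratio: 100% / 80% = 1.25, whatever the home dose.
- With an assumed home dose of 60 U/day: 1.00 × 60 = 60 U against 0.80 × 60 = 48 U, a difference of 12 U.
- Qualification: X.a also mentions a reduced start of 0.3 U/kg for patients aged 70 or over or with eGFR below 60, without limiting it to insulin-naive patients as IV.f does. If it is read to cover home-insulin patients, the ratio for them depends on weight and home dose, and 1.25 does not apply.
- Range affected: above 200 to below 400 mg/dl, which is 200 of the 260 mg/dl eligible width (200/260 = 0.77). This is a width only; the documents do not give the share of patients in it.

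**3. Discharge at A1C of 10% or more**

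| Earlier therapy | Aim 2 | V.b | Same regimen? |
|---|---|---|---|
| None | basal bolus | half of inpatient basal dose | No |
| Oral drugs, no contraindication | basal bolus | oral drugs + glargine at 80% of inpatient dose | No |
| Oral drugs + basal insulin, no contraindication | basal bolus | oral drugs + glargine at 80% of inpatient dose | No |
| Oral drugs contraindicated | basal bolus | basal bolus at 100% of inpatient dose | Yes |
| Basal bolus | basal bolus | basal bolus (dose: step 4) | Yes |

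Aim 2 gives no dose, so the conflict is one of regimen and no dose difference can be computed.

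**4. A lesser ambiguity inside V.b**

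Patients previously on basal bolus alone appear in an exception inside an oral-drug bullet, at 100% of the inpatient dose. They also fall under the closing line of V.b, at 50% to 80% of the preadmission TDD. The two use different dose bases, so neither is always larger. With an assumed home dose of 60 U:

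- Closing line: 0.50 × 60 = 30 U to 0.80 × 60 = 48 U.
- Exception, with an assumed inpatient dose of 48 × 0.80 = 38.4 U (an 80% start and one 20% cut): 38.4 U.
- 38.4/48 = 0.80 and 38.4/30 = 1.28, so the exception lies 20% below the upper figure and 28% above the lower.

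**The case against.** The strongest reply is that both conflicts set a summary against its detail. IV.d introduces its account as brief, and Aim 2 is an aims statement. IV.f and V.b are titled as the treatment protocol and the discharge algorithm, and sites may well work from them. A figure under the Aim 2 heading in section V is also missing from the text reviewed and could bear on the discharge regimen. This has weight for IV.d and for Aim 2. It does not account for X.a, which presents the 20% reduction as an actual safeguard and then allows the physician to go further. The missing figure cannot remove the difference between the two written rules.

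A second reply is that the consequences are small, and most of this stands. Randomization is blocked on prior insulin use, so affected patients should be balanced between arms. The primary outcome leaves out the first day of therapy, and dose adjustment starts on day 2. Dose cuts follow glucose of 70–99 and below 70 mg/dl, and the DSMB meets every six months. Hypoglycemia, however, is recorded from day 1. The stated discretion does not settle the starting dose either: X.a allows further reduction in severe hypoglycemia, and Appendix 1 ties the team's discretion to glucose below 70 or above 350 mg/dl.

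The gap at exactly 200 mg/dl and the overlap within V.b are fairly called drafting ambiguities. They are included because the same edit resolves them.

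**Conclusion.** The concern holds. Above 200 mg/dl, IV.f conflicts with IV.d and X.a on the starting dose for home-insulin patients, by a factor of 1.25, subject to how the 0.3 U/kg rule is read. At an A1C of 10% or more, Aim 2 and V.b give different regimens to patients on oral drugs without contraindications and to previously untreated patients.

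The effect on the trial's inference is limited. The rules are common to both arms, and no between-arm bias, loss of power or difference in site practice is shown. The number of patients affected is unknown, and the unit figures rest on assumed doses. The correction should be made because the rules cannot all be followed for the same patient and the stated safeguard does not match the treatment protocol. No view is taken on which dose or regimen is right.

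**What to change.** - Reconcile IV.d, IV.f and X.a to one starting-dose rule for patients on insulin before admission, covering a glucose of exactly 200 mg/dl. State whether the reduced start for older patients or reduced eGFR applies to them.
- Reconcile Aim 2 with V.b, and the overlapping lines within V.b, so that each combination of HbA1c and earlier therapy, including no earlier drug treatment, has one discharge rule and one stated dose base (inpatient or preadmission).
- The clinical team decides which rules stand. The risk section is then aligned with them, and sites and the IRB are notified.

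The cost is amendment wording and notification, with no extra patients or procedures.

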In the Rabbit-Surgery trial (Figure 2), 211 general non-cardiac surgery patients with T2D were randomized to a basal bolus (BB) with glargine once daily and glulisine before meals and to sliding scale regular insulin (SSI). Study outcomes included differences in daily BG levels and a composite of hospital complications including postoperative wound infection, pneumonia, respiratory failure, acute renal failure, and bacteremia. The mean daily glucose after the 1st day of BB and SSI was 145±32 mg/dl and 172±47 mg/dl, respectively, p<0.01. BG readings <140 mg/dl were recorded in 55% of patients in BB and 31% in the SSI group, p<0.001. There were reductions with BB as compared with SSI in the composite outcome (24.3% and 8.6%, OR: 3.39 (95% CI: 1.50-7.65); p=0.003). We concluded that treatment with BB improved glycemic control and reduced complications compared to SSI in surgery patients with T2D.

Basal insulin during Hospital Discharge.(36)

Fig 1

Mean Blood Glucose Levels During Basal Bolus and SSRI

[figure not shown]

Figure 3. Postoperative Complications

[figure not shown]
[figure not shown]
[figure not shown]

Fig 3. Discharge Insulin Algorithm
* Composite of pneumonia, respiratory failure, acute renal failure, and bacteremia.

In a recent preliminary study we assessed the efficacy of an HbA_{1c} based algorithm for the management of non-ICU insulin treated patients with T2D (Fig. 4). A total of 214 general medicine and surgery patients with an admission HbA_{1c} < 7% were discharged on their same outpatient antidiabetic regimen (oral antidiabetic drugs, OAD and/or insulin). Patients with an HbA_{1c} between 7% and 9% were discharged on a combination of OADs and basal (glargine) insulin at 50% of total daily hospital dose. Patients with an admission HbA_{1c} ≥ 9% were discharged on a combination of oral agents and basal insulin at 80-100% of total daily hospital dose or on a basal bolus regimen at the same hospital dosage. The admission HbA_{1c} of 8.75% decreased to 7.9% and 7.35% after 4 and 12 weeks of hospital discharge respectively (p<0.01, Fig 5). Patients with higher HbA_{1c} levels experienced a greater reduction as well as those treated with basal bolus insulin regimens. We concluded that the admission HbA_{1c} concentration is beneficial in designing the discharge treatment algorithm after discharge in non-ICU patients with T2D.

Change in HbA_{1c} levels after discharge

Umperiez et al. ADA Scientific Meeting, Philadelphia 2012

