The primary outcome of the study is to determine differences in glycemic control as measured by mean daily blood glucose concentration between treatment groups. For each subject, we will take the average of all pre-meal and bedtime glucose values collected after the first day of therapy during the hospital stay (up to 10 days).

Secondary outcomes include differences between treatment groups in any of the following measures:

1. Differences in mean daily glucose in patients admitted to medicine and surgery services.
2. Differences in mean daily glucose in patients with admission HbA1c lower than and higher than 8%.
3. Differences in mean daily glucose in patients with length of stay shorter and longer than 3 and 5 days.
4. Proportion of BG readings within target of 80 mg/dl and 180 mg/dl before meals.
5. Number of BG readings between 80 mg/dl and 180 mg/dl before meals without hypoglycemia.
6. Number of patients with hypoglycemia (defined as a BG < 70 mg/dl) and number of events adjusted by length of stay (event rate).
7. Number of patients with severe hypoglycemia (defined as a BG < 40 mg/dl) and number of events adjusted by length of stay (event rate).
8. Length of hospital stay.
9. Cardiac complications are defined as myocardial infarction, cardiac arrhythmia requiring medical treatment, or cardiac arrest.
10. Acute renal failure defined as a clinical diagnosis with documented new-onset abnormal renal function (increment in serum creatinine > 0.5 mg/dL from baseline).
11. Hospital mortality.

IV.d. Plan. This study will include male or female subjects > 18 years. Due to the design of this study, there will be no run-in period. Upon arrival to the emergency department or medical or general surgical wards, subjects will be screened. Patients with a known history of T2D treated with diet alone, any combination of OADs, and insulin prior to admission will be considered potential candidates for this study. Patients treated with degludec, glargine U300 or with long-acting GLP1-RA (dulaglutide, albiglutide and weekly exenatide) prior to admission will be excluded. Patients admitted with acute or chronic medical illnesses, emergency or elective surgical procedures and trauma would be included in the study. The goal of insulin therapy is to maintain fasting and pre-meal blood glucose levels between 80 mg/dl and 180 mg/dL while avoiding hypoglycemia.

A total of 180 patients with T2D with a blood glucose > 140 mg/dL and < 400 mg/dL will be randomized to receive:

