- If a patient develops hypoglycemia (BG <70 mg/dL), the insulin TDD (basal and prandial) should be decreased by 20%.
- If a patient develops severe hypoglycemia (BG <40 mg/dL), the insulin TDD (basal and prandial) should be decreased by 30-40%.

IV.g. Data Analysis:

Aim 1. To determine differences in inpatient glycemic control, as measured by mean daily blood glucose concentration and frequency of hypoglycemia, in general medicine and surgery patients with T2D treated with basal bolus regimen with glargine U300 and U100 plus glulisine insulin before meals.

Due to the lack of efficacy and safety data with the use of glargine U300 in the inpatient setting, periodic conduct interim analyses will be conducted every 6 months to monitor the primary outcome and rate of hypoglycemia, and to modify the study design regarding interval of administration and dosage adjustment for basal insulin (see page 9, Data Safety Monitoring Plan, sections IV. f. and IV.g.).

Sample Size and Power Calculations:

The primary endpoint in this study is glycemic control measured by mean daily BG concentration. To show the non-inferiority of glargine U300 and U100 in terms of glycemic control, we set the equivalence margin as 18 mg/dl (1 mosm/l), from a view that a difference <18 mg/dl is usually not considered as clinically significant (12, 14, 16). Based on the results from Rabbit medicine and surgery trials, it is reasonable to assume the standard deviation of mean daily BG is bounded above by 45 mg/dl. Assuming the true BG difference between the treatment groups is zero, and using one-sided, two-sample t-tests, we require 78 subjects for each treatment group to achieve 80% power. Accounting for 10% attrition rate, we would need 90 patients per treatment group, which means 180 subjects in total, to achieve >80% power in Aim 1.

Analysis of Primary Endpoint:

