The primary endpoint for Aim 1 is glycemic control measured by mean daily BG concentration among the two study groups. Blood glucose will be measured before each meal and at bedtime. We will first perform cross-sectional analyses using nonparametric Krustal-Wallis tests (or Wilcoxon tests) or one-way ANOVA, followed by repeated measures ANOVA to estimate and test the difference between the two treatment groups while simultaneously examining mean daily BG across multiple days during treatment. A mixed effect model may be used to further account center effect or other potential confounders for the BG outcome. Stepwise, backward, or forward model selection strategy will be adopted to determine the variables to be included in the final model. Standard diagnostic and model checking procedures will be applied to examine the fit of the developed models.

Analysis of Secondary Endpoints:

Secondary endpoints for Aim 1 in this study include incidence of hypoglycemia, number of hypoglycemic

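### The trial is sized for non-inferiority within 18 mg/dL, but the primary analysis only tests for a difference and states no margin comparison, alpha or success rule

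*Combined protocol and SAP*

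**What the plan says.** **Objective.** The Aim 1 hypothesis under Specific Aims reads: "Treatment with glargine U300 will result in equivalent glycemic control in hospitalized patients with T2D". The sample size text in IV.g (Data Analysis) names a different target: "To show the non-inferiority of glargine U300 and U100 in terms of glycemic control, we set the equivalence margin as 18 mg/dl". Section IV.c describes the primary outcome as a difference between groups.

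**Sizing.** IV.g assumes a true difference of zero and says "it is reasonable to assume the standard deviation of mean daily BG is bounded above by 45 mg/dl". It concludes: "using one-sided, two-sample t-tests, we require 78 subjects for each treatment group to achieve 80% power". With 10% attrition this becomes 90 per arm, 180 in total. No alpha is given.

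**Endpoint.** IV.c defines one value per patient: "For each subject, we will take the average of all pre-meal and bedtime glucose values collected after the first day of therapy".

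**Analysis.** Analysis of Primary Endpoint, also in IV.g, begins "We will first perform cross-sectional analyses using nonparametric Krustal-Wallis tests (or Wilcoxon tests) or one-way ANOVA". The second step in that section is worded as "followed by repeated measures ANOVA to estimate and test the difference between the two treatment groups". A mixed model with data-driven covariate selection is optional. The margin is not mentioned.

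**Aim 2.** V.g.1 reuses the margin and SD for sizing. V.g.2 lists t-tests, Wilcoxon tests or ANOVA, then regression, again without the margin.

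**Alpha.** The only level in the document is two-sided, below 0.01. It belongs to the stopping rule on death and hospital complications.

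**The concern.** A test for a difference and a test against a margin answer different questions. The first asks whether the data rule out zero, and a non-significant result may only mean low precision. The second asks whether the data rule out a deficit of 18 mg/dL or more, which is the question the trial was sized for.

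The listed analyses are all of the first kind. The rank tests named first for Aim 1 do not even give a mean difference in mg/dL to set against 18. The repeated measures ANOVA does give an estimate, so the data can answer the question, but nothing tells the analyst to make the comparison.

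Two things are at stake. The trial could report no difference without having met its own margin. And because test, alpha, covariates and success rule are all open in an open-label trial, they could be settled after the data are seen. The shift between equivalent and non-inferior adds to this, because the two targets have different power at the planned size.

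**Working it through.** **Inputs.** From IV.g: margin 18 mg/dL, SD 45 mg/dL (an upper bound), true difference 0, one-sided two-sample t-test, 80% power, 10% attrition, 90 enrolled per arm. From III (Preliminary Results): "The mean daily glucose after the 1st day of BB and SSI was 145±32 mg/dl and 172±47 mg/dl". Reading ± as SD, the basal bolus arm gives 32. SD 40 is my intermediate value.

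**1. Reproduce the plan's 78 per arm.** Normal approximation: n = 2 × [SD × (z(1−α) + z(0.80)) / margin]².

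- One-sided α 0.05: 2 × [45 × (1.645 + 0.842) / 18]² = 77.3, so 78. The exact noncentral t calculation also gives 78, with power 0.800.
- One-sided α 0.025: 99 by the normal formula and 100 by the t calculation.

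So the plan's figure implies one-sided 0.05, which the plan does not state. For attrition, 78 / 0.9 = 86.7, so 87; the plan rounds up to 90. That leaves 90 × 0.9 = 81 evaluable per arm and non-inferiority power of 0.813.

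**2. Compare the two decision rules at 81 per arm.** SE = SD × √(2/81), with 160 degrees of freedom. The plan gives no rule, so I assume that a non-significant two-sided 5% test would be read as success.

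- The difference test is non-significant when the observed difference is below t(0.975) × SE in absolute value.
- Non-inferiority is shown when the observed U300 minus U100 difference is below 18 − t(0.95) × SE.
- Between these two limits the result is not different, yet non-inferiority fails. At SD 45, SE = 7.07, so the zone runs from 18 − 1.654 × 7.07 = 6.3 to 1.975 × 7.07 = 14.0 mg/dL.

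The false-claim rate is the noncentral t probability of a non-significant result at a true difference of 18. The chance of ending in the zone comes from 400,000 simulations at a true difference of 0.

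| | SD 45 | SD 40 | SD 32 |
|---|---|---|---|
| SE (mg/dL) | 7.07 | 6.29 | 5.03 |
| Non-inferiority power, one-sided 0.05, true difference 0 | 0.813 | 0.886 | 0.973 |
| False claim from a non-significant difference test, true deficit 18 | 28.4% | 18.8% | 5.5% |
| False claim from the margin test, true deficit 18 | 5% | 5% | 5% |
| Zone: not different, but non-inferiority not shown (mg/dL) | 6.3 to 14.0 | 7.6 to 12.4 | 9.7 to 9.9 |
| Chance of ending in the zone when the insulins are identical | 16% | 9% | 0.6% |

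**3. If two-sided equivalence is meant.** Both limits of the 90% interval must lie within ±18. Power at a true difference of 0 is then 0.627 (SD 45), 0.772 (SD 40) and 0.945 (SD 32) at 81 per arm, and 0.600 at 78 per arm with SD 45. Reaching 80% at SD 45 takes 2 × [45 × (1.645 + 1.282) / 18]² = 107.1, so 108 evaluable per arm.

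**The case against.** The strongest reply is that the sample size paragraph sits under the same IV.g heading, directly before the analysis text, and names the objective, the margin and a one-sided t-test. Read together, the two paragraphs let a statistician infer a margin test. The repeated measures ANOVA (Aim 1) and the t-test and regression (Aim 2) would also yield a mean difference and standard error to set against 18. This stands as a reading of intent. It does not supply the alpha, the confidence level or the success rule, and the section that governs the primary analysis prescribes something else.

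Second, the 28% figure rests on a reading the plan does not contain and on an SD the plan calls an upper bound. Both points are fair. At SD 32 the false-claim rate is 5.5% against 5%, and the conflict zone is about 0.25 mg/dL wide. But 32 comes from one arm of one surgical trial, and the plan chose 45 for sizing.

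Third, one-sided 0.05 is inferred. At one-sided 0.025, power at 81 per arm and SD 45 would be about 72%, so the claim that no patients need be added depends on keeping 0.05.

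Fourth, Aim 2 takes only Aim 1 patients with HbA1c of at least 7.5% who accept an invitation, so 90 per arm is unlikely to be available. If 50 per arm were evaluable (an assumption), power at SD 45 would be about 63%. That is a separate sizing problem; it does not make the margin rule wrong for Aim 2.

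**Conclusion.** The concern holds and must be fixed. The sample size is right for non-inferiority at one-sided 0.05; the fault is that the analysis text does not test what the trial was sized to show, for either aim. The absence of a margin comparison, primary alpha and success rule does not depend on any assumption.

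The size of the harm does. It rests on non-significance at two-sided 5% being taken as success, and on the SD. The excess false-claim risk is 28% against 5% at the planning SD of 45, and close to nothing at 32. The stated 80% power does not carry over to equivalence at the planning SD, where it would be about 60% at 78 per arm and 63% at 81.

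**What to change.** In IV.g, make the primary analysis the U300 minus U100 difference in the patient-level mean daily glucose defined in IV.c, with a two-sided 90% confidence interval. State the one-sided alpha of 0.05. Claim non-inferiority if the upper limit is below 18 mg/dL, judged once, at the final analysis. Label the rank tests, ANOVA, repeated measures and mixed models as supportive. Put the same rule in V.g.2 for Aim 2.

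Use one word for the objective throughout. Non-inferiority is what the sample size supports, so the hypothesis should change from equivalent to non-inferior. If the sponsor keeps equivalence, require both limits within ±18 mg/dL and restate power: about 60% at 78 per arm and 63% at 81 with SD 45, and, at 81 per arm, about 77% with SD 40 and 94% with SD 32.

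The cost is wording in the hypotheses, IV.g and V.g, with no added patients or data. The downside is that the claim is limited to non-inferiority at one-sided 0.05, or a lower power is stated for equivalence. Moving to one-sided 0.025 instead would need 100 evaluable per arm (100 / 0.9 = 111.1, so 112 enrolled) for 80% power at SD 45.
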